For this study we will use a mixed within- and between subject design to examine effects of THC (0 and 15 mg) in two groups of female occasional cannabis users: women tested in the early follicular phase of their menstrual cycle (EFG; N=30) and women tested in the late follicular phase (LFG; N=30). Occasional cannabis users will be defined as individuals who have used cannabis 10 or less occasions in the past thirty days. Females will be randomly assigned EFG or LFG groups. EFG women will be tested 1 to 8 days since the first day of menstruation and LFG women between days 9 and 14. Subjects will attend two four-hour experimental sessions in which they receive THC (15 mg THC) or placebo in counterbalanced order under double blind conditions. Plasma and saliva samples will be obtained before capsule consumption at the start of each session for baseline hormone, endocannabinoid and cortisol levels. The primary outcome measure is salivary cortisol, which will be measured both at baseline and periodically post-drug consumption. Secondary outcome measures include heart rate, blood pressure, body temperature, subjective drug effects (i.e. "feel drug effect"), and THC-induced anxiety. For Aim 1 we will examine THC-induced increases in cortisol in relation to baseline estradiol levels. For Aim 2 will examine THC-induced cortisol in relation to baseline endocannabinoid levels. For Aim 3 we will examine THC-induced increases in heart rate and subjective drug effects relative to THC-

induced increases in cortisol. The study will be approved by the Institutional Review Board at the University of Chicago, in accordance with the Code of Federal Regulations (Title 45, Part 46) adopted by the National Institutes of Health and the Office for Protection from Research Risks of the US Federal Government. The studies will be conducted in accordance with the Helsinki Declaration of 1964 (revised 1989) and the National Advisory Council on Drug Abuse Recommended Guidelines for the Administration of Drugs to Human Subjects.

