Statistical Analyses Sample Size Calculation: Sample size calculations were conducted using G*Power3.1 Software. Since there are no published data on effects of estradiol or eCB levels on response to THC a small effect size was assumed ($d = 0.3$). Recruiting 30 participants for each experimental group, 30 females in early follicular phase, 30 females in late follicular phase, for this study will allow for 80% power to detect an effect at alpha level $p = 0.05$.

A multilevel longitudinal mediation model will be used to analyze the collected data. Our independent variables include within-subjects drug dose and between subjects estradiol (EFG or LFG), AEA and 2-AG levels. Our mediator variable is subjective anxiety across session time. Our dependent outcome measures include heart rate, blood pressure and salivary cortisol across session time. A multilevel longitudinal mediation model will allow for the determination of how drug condition and baseline estradiol, AEA and 2-AG levels affects subjective anxiety across session time, which mediates changes in heart rate, blood pressure and salivary cortisol.

Expected Outcomes Based on several preclinical studies, I expect the LFG to have higher levels of estradiol and anandamide at baseline than the EFG, but no significant differences in baseline trait anxiety, anxiety sensitivity or salivary cortisol (Reed and Carr, 2000; Gorzalka and Dang, 2012; Monero-Lopez et al. 2018). Further, I expect that the effect of THC on subjective anxiety, heart rate and salivary cortisol will be greater in the LFG compared to the EFG, even after including any possible baseline differences in cortisol, trait anxiety or endocannabinoids as a covariate. Additionally, based on preliminary data and prior literature, I expect females with lower endocannabinoid levels, after controlling for cycle phase or estradiol levels, to experience larger increases in subjective anxiety, heart rate and report significantly greater subjective drug and mood effects of oral THC in a dose dependent manner (Hill et al. 2010). Finally, I expect THC-induced change in cortisol to mediate the increase in heart rate and greater subjective drug and mood effects. These results will contribute significantly to the small literature on individual differences in response to THC and lay a foundation for future

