sex-specific cannabis use guidelines, to prevent against THC-induced anxiety, paranoia, and psychosis, and new sex-specific cannabis use disorder treatment options.

Potential problems, Alternative strategies, and Limitations Several problems could arise. First, it may be difficult to recruit qualifying participants in the planned time frame. This seems unlikely since similar inclusion criteria have been used in prior studies within the lab and there has not been significant difficulty recruiting these individuals. But if this is the case, I will increase venues for advertising and identify new online recruitment sources. Second, the differences in responses to THC in females at different phases of their menstrual cycle may be too small to detect with this sample. This is possible, even though we based the sample size on a small effect size. If the findings look promising we would consider increasing our sample size or utilize the data as a pilot for a future study with a larger sample. Third, the two groups of females may differ in pre-capsule measures, such as mood states, cortisol levels, eCB levels, blood pressure or in demographic characteristics such as prior drug use. I will include any of these significant differences between groups as a covariate in the final analyses.

Literature Cited

American Psychiatric Association. (2013). Cautionary statement for forensic use of DSM-5. In *Diagnostic and statistical manual of mental disorders* (5th ed.). doi:10.1176/appi.books .9780890425596.744053

Craft, R. M., & Leitl, M. D. (2008). Gonadal hormone modulation of the behavioral effects of Δ9-tetrahydrocannabinol in male and female rats. *European Journal of Pharmacology*, 578(1), 37–42.

Crean, R. D., Crane, N. A., & Mason, B. J. (2011). An Evidence Based Review of Acute and Long-Term Effects of Cannabis Use on Executive Cognitive Functions. *Journal of Addiction Medicine*, 5(1), 1–8. <https://doi.org/10.1097/ADM.0b013e31820c23fa>

D'Souza, D. C., Ranganathan, M., Braley, G., Gueorguieva, R., Zimolo, Z., Cooper, T., ... Krystal, J. (2008). Blunted Psychotomimetic and Amnestic Effects of Δ-9-Tetrahydrocannabinol in Frequent Users of Cannabis. *Neuropsychopharmacology*, 33(10), 2505–2516. <https://doi.org/10.1038/sj.npp.1301643>

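### The plan leaves open enlarging the study if findings look promising, with no trigger, outcome, second-stage size or error control; if used with an ordinary pooled retest, the false-positive rate exceeds 5%

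*Combined protocol and SAP*

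**What the plan says.** The section Potential problems, Alternative strategies, and Limitations raises the possibility that differences in THC response "at different phases of their menstrual cycle may be too small to detect with this sample". It then says: "If the findings look promising we would consider increasing our sample size or utilize the data as a pilot", the pilot being for a later, larger study. Enlarging the sample is listed as an alternative to that pilot, so the natural reading is that participants would be added to this study.

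Sample Size Calculation, under Statistical Analyses, sets 30 women per phase group and states that this "will allow for 80% power to detect an effect at alpha level" 0.05, with d = 0.3. Sidedness, test family and the correlation between sessions are not given.

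On outcomes, Approach states: "The primary outcome measure is salivary cortisol, which will be measured both at baseline and periodically post-drug consumption". Expected Outcomes predicts that "the effect of THC on subjective anxiety, heart rate and salivary cortisol will be greater in the LFG compared to the EFG". The analysis paragraph lists heart rate, blood pressure and cortisol as dependent outcomes and anxiety as mediator.

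Nowhere does the document say what counts as promising, which outcome would decide, how many participants would be added, how the two stages would be combined, or how the error rate would be controlled.

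**The concern.** A decision to add participants because a non-significant result leans the right way gives the hypothesis a second chance. If the first look can already declare success at 0.05, and the pooled data are tested again at 0.05 after an extension, the two chances together exceed 5%.

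The hypothesis is directional (late follicular above early follicular), so a trend that way is the result most likely to look promising. The added false positives would then fall mainly in the predicted direction, and a reported phase effect could not be taken at its stated error rate. With several outcomes in play, the freedom to choose which one looks promising adds to this.

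**Working it through.** **The plan's own figure.** Sample Size Calculation claims 80% power with 30 per group at d = 0.3 and alpha 0.05. A two-group comparison has noncentrality 0.3 × √(30/2) = 1.162. Two-sided power is about 21% (normal 21.3%, t test 20.8%), so 80% is not reproduced. Roughly 80% does appear under some repeated-measures inputs that the plan does not state, such as a within-between interaction with f = 0.15, two measures and correlation near 0.67. That is a separate matter. Here the 21% serves only as the baseline of the proxy.

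**Inputs from the plan.** 30 per group at the first look; alpha 0.05; d = 0.3; predicted direction LFG above EFG.

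**Assumptions, because the plan states none.** One outcome; a two-group comparison standing in for the phase contrast; two-sided 0.05 at both looks; a single extension of n₂ = 15 or 30 per group (total 90 or 120); success can be declared at 60; pooled retest. Promising means a first-look p above 0.05 but below a cut-off P.

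**Formula.** With z₁ from the first 60 and z₂ from the added participants, the pooled statistic is w₁z₁ + w₂z₂, where w₁ = √(30/(30+n₂)) and w₂ = √(n₂/(30+n₂)). Under no effect, extending favourable trends only:

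error = 0.05 + ∫ φ(x) [1 − Φ((1.96 − w₁x)/w₂) + Φ((−1.96 − w₁x)/w₂)] dx, for x from Φ⁻¹(1 − P/2) to 1.96.

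Extending in either direction doubles the integral. For n₂ = 30, w₁ = w₂ = 0.707. With P = 0.10 the integral is 0.0041, giving 5.41%. With any favourable trend it is 0.0166, giving 6.66%.

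| First-look p below | Favourable only, N = 90 / 120 | Either direction, N = 90 / 120 | False positives in predicted direction, favourable only |
|---|---|---|---|
| 0.10 | 5.49 / 5.41% | 5.97 / 5.82% | 2.99 / 2.91% |
| 0.20 | 5.94 / 5.88% | 6.89 / 6.76% | 3.44 / 3.38% |
| 0.50 | 6.29 / 6.42% | 7.58 / 7.85% | 3.79 / 3.92% |
| 1 (any trend) | 6.35 / 6.66% | 7.70 / 8.31% | 3.85 / 4.12% |

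The last column compares with 2.5% for a single two-sided test. Simulated t tests with doubling and either-direction extension gave 5.9%, 6.7% and 7.3% for cut-offs 0.10, 0.20 and 0.30; the integration gives 5.8%, 6.8% and 7.3%.

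**Sensitivity.** Adding 10 to 120 per group moves the favourable-only range to about 5.2-7.1%. At 120 added per group, extending every non-significant result gives 9.2%. If 0.05 is one-sided, with one-sided cut-offs 0.10 to 0.50 and totals of 90-120, the range is 6.0-7.9%.

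**Power at d = 0.3, same proxy, favourable trends extended.** No extension: about 21%. Extension to 90: 26-34%. Extension to 120: 27-42%. Part of the gain comes from the inflated error.

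**With control.** Nominal two-sided 0.0294 at 60 and at 120 (critical value 2.178) gives overall error of 5.00% if every non-significant result is extended, and 3.35-3.97% if only favourable trends are. Power at the first look is about 1 − Φ(2.178 − 1.162) = 15.5%, and overall 23-33%. The smallest significant difference at 60 rises from t × √(2/30) = 0.517 SD to 0.577 SD.

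**The case against.** The strongest reply is that this is not a planned analysis. The sentence sits among limitations, says only that enlargement would be considered, and offers a pilot in the same breath. That pilot does no harm if the later study is analysed without these data. The size is 60 wherever the design is described. The plan nowhere says the stages would be pooled or retested at 0.05; both steps are supplied here. If no success could be declared at 60, this inflation would not arise. All of this stands, and it is why the point is minor. It does not remove the gap: the sentence takes up the case where the difference was not detected at 60, which presupposes a test there, and nothing restricts what may follow.

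The second reply is that 5% is itself idealised. Alpha appears only in the sample-size statement, the stated analysis is a multilevel mediation model with several outcomes, and no single phase test is specified. Three independent tests at 0.05 would already give 1 − 0.95³ = 14% (illustrative only, since these outcomes are correlated). Beside that, 0.4 to 1.7 points is small. This also stands as to size, and it is a reason to name the primary contrast in the fix.

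A reader might infer that the trial has an inflated error rate as designed, or that 5.4-6.7% is a property of the plan. The documents support neither: the option may never be used, and the range comes from assumptions made here. Nor is 8.3% a general ceiling, because a larger second stage raises it.

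**Conclusion.** The point holds as a conditional one, and it is minor. The plan keeps open a results-dependent enlargement without defining it. If that option is used with success also possible at 60 and an unadjusted pooled retest, the false-positive rate exceeds 5%. Confidence in that direction is high; confidence in whether the option would be used, and in the exact size, is low. Under the stated assumptions the excess is modest: about 5.4-6.7% overall if only favourable trends are extended, and up to 8.3% for extensions to at most 120 if every non-significant result is. If the option is not exercised, the analysis at 60 is unaffected.

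**What to change.** Replace the sentence in the limitations section with:

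> The LFG-EFG difference in THC-minus-placebo salivary cortisol (primary outcome) is tested at N = 60. The sample for this and the other phase comparisons will not be increased after results have been seen. Promising data may serve as a pilot for a future study analysed without them.

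The edit is one sentence's worth of text, but it is not free: it gives up the power that an extension could add, shown above for the proxy.

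If the investigators prefer to keep an extension, they should pre-specify the same endpoint and contrast, one look at 60, a fixed total of 120, and nominal two-sided 0.0294 at both looks. Overall error for that contrast is then at most 5.0% under the two-look proxy. The costs are up to 60 more participants, a stricter test at 60, and a rule that is conservative if only favourable trends are extended.

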Aim 1: To examine whether high levels of estradiol augment the effect of THC on subjective anxiety, heart rate, blood pressure and salivary cortisol in females. To test this, female occasional cannabis users will receive a single dose of THC (0, 15 mg) during either the early follicular phase (days 1-8) when estradiol levels are low, or during the late follicular phase (days 9-14) when estradiol levels are high. Participants will attend two experimental sessions separated by at least four days, to allow for clearance of the drug. Plasma levels of estradiol, progesterone, and endocannabinoids, as well as salivary cortisol, physiological measures and subjective mood ratings will be obtained at the beginning of all three sessions. During the sessions, physiological measures, subjective ratings of drug effects and mood, and salivary cortisol will be obtained at regular intervals after drug consumption. I hypothesize THC will produce a greater increase in subjective anxiety, heart rate, blood pressure and salivary cortisol during the late follicular phase, and that this will be correlated with higher circulating levels of estradiol.

Aim 2: To examine whether low levels of circulating endocannabinoids augment the effects of THC on subjective anxiety, heart rate, blood pressure and salivary cortisol in females. To test this, the plasma samples mentioned above will also be analyzed for endocannabinoids, anandamide (AEA) and 2-arachidonoylglycerol (2-AG) levels. Baseline AEA and 2-AG levels will be compared to THC-induced increases in subjective anxiety, heart rate, blood pressure and salivary cortisol. I hypothesize females with lower endocannabinoid levels will exhibit greater THC-induced increases in subjective anxiety, heart rate, blood pressure and salivary cortisol levels.

Aim 3: To evaluate determine whether subjective anxiety mediates the physiological stress response after THC. To test this, I will use a multilevel longitudinal mediation model to analyze the collected data. Our independent variables will include within-subjects drug dose and between subjects estradiol (EFG or LFG), AEA and 2-AG levels. Our mediator variable will be subjective anxiety across session time. Our dependent outcome measures include heart rate, blood pressure and salivary cortisol across session time. A multilevel

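### Aim 1 does not say whether it reports the total or the endocannabinoid-adjusted phase effect, and the significance rule for covariates can let the observed anandamide difference decide

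*Combined protocol and SAP*

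**What the plan says.** **The covariate rule.** Potential problems, Alternative strategies, and Limitations foresees that the early (EFG) and late (LFG) follicular groups may differ in "mood states, cortisol levels, eCB levels, blood pressure or in demographic characteristics such as prior drug use". It then says: "I will include any of these significant differences between groups as a covariate in the final analyses". It gives no significance level for that test, and no section names a fixed covariate set.

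**The model.** Statistical Analyses says: "A multilevel longitudinal mediation model will be used to analyze the collected data". It continues: "Our independent variables include within-subjects drug dose and between subjects estradiol (EFG or LFG), AEA and 2-AG levels". No condition is attached to the two eCB terms. Aim 3 introduces the same model as the way to test mediation.

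**Aim 1.** The Approach says: "For Aim 1 we will examine THC-induced increases in cortisol in relation to baseline estradiol levels". Aim 1 itself compares the two phase groups and also expects a correlation with circulating estradiol. Neither place mentions eCB adjustment. The Approach assigns women to phase at random.

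**The expected relations.** Expected Outcomes says: "I expect the LFG to have higher levels of estradiol and anandamide at baseline than the EFG". Aim 2 says: "I hypothesize females with lower endocannabinoid levels will exhibit greater THC-induced increases in subjective anxiety, heart rate, blood pressure and salivary cortisol levels". Expected Outcomes also predicts that the larger LFG response will persist "even after including any possible baseline differences in cortisol, trait anxiety or endocannabinoids as a covariate".

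**The concern.** On the plan's own hypotheses, being tested in the late follicular phase does two things. It enlarges the THC response, and it raises AEA, which should dampen that response. The total phase effect contains both. Adjusting for AEA removes the dampening part and leaves a larger effect. These answer different questions, and a reader of the results would need to know which one is reported.

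The covariate rule makes this worse. If AEA is a candidate under it, the AEA difference observed in 60 women decides which effect appears as the Aim 1 result.

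A lesser matter concerns covariates that phase does not affect. After random assignment, a test of group difference says little about whether a variable predicts the response, so the rule usually omits useful covariates.

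**Working it through.** **Inputs.** From the documents: 30 women per group, random assignment to phase, d = 0.3, alpha 0.05. Assumed, because the documents are silent: two-sided tests, the size of the AEA shift, the AEA slope, the covariate correlations, and the screening level. Effects are in SD units of the per-woman THC-minus-placebo response.

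**1. The plan's own figure.** For a two-group comparison, the noncentrality is d√(n/2) = 0.3 × √15 = 1.162 on 58 df, giving 20.8% power rather than the stated 80%. About 80% appears only under repeated-measures settings that the plan does not state, such as f = 0.15 with two measures correlated at about 0.65 to 0.68. That is a separate matter, and this point does not rest on it.

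**2. What the rule requires.** At p < 0.05, a covariate enters when the group difference exceeds t(0.975, 58) × √(2/30) = 2.002 × 0.2582 = 0.517 SD. A variable with no true difference is therefore left out in about 95% of trials.

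**3. Total and adjusted effects.** If AEA enters with a drug interaction, or as a covariate on a change score:

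adjusted = total + slope × shift

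Here the slope is the fall in response per SD of AEA. With total 0.30, slope 0.4 and shift 0.5, adjusted = 0.30 + 0.4 × 0.5 = 0.50.

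The chance that the rule triggers has noncentrality 0.5 × √15 = 1.936, giving 47.8% (47% to 48% in simulation). The mean estimate is about 0.50 when it triggers and 0.376 when it does not. Overall: 0.48 × 0.50 + 0.52 × 0.376 = 0.44. Repeat simulations gave 0.43 to 0.44. Neither branch averages the total of 0.30, because the untriggered trials are those with a small observed AEA difference.

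| AEA shift, slope | Adjusted | Under the rule (p < 0.05) |
|---|---|---|
| 0, 0.4 | 0.30 | 0.30 |
| 0.3, 0.2 | 0.36 | 0.33 |
| 0.5, 0.4 | 0.50 | 0.44 |
| 1.0, 0.4 | 0.70 | 0.70 |

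For shift 0.5 and slope 0.4, screening at 0.10 or 0.20 gives 0.46 or 0.48.

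With the same shift and slope but a true total of zero, the phase test rejects in about 5% of trials unadjusted, 8% under the rule and 13% always adjusted. The adjusted effect is then truly 0.20, so these are not false positives for that effect. They mislead only if read as evidence of a total effect.

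**4. Main effect only.** One AEA value per woman, entered without a drug interaction, adds the same amount to both of her sessions. It cancels from THC minus placebo, and drug-by-phase does not move.

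**5. Covariates that phase does not affect.** Power at d = 0.3, 40,000 runs per cell, screen at p < 0.05:

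| Correlation r with the response | Rule | Fixed adjustment |
|---|---|---|
| 0 | 20.9% | 20.6% |
| 0.3 | 20.5% | 22.3% |
| 0.5 | 20.5% | 26.0% |

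Mean estimates were 0.299 to 0.302 for a true 0.30. Under the null, the rule's type I error was 5.2%, 4.7% and 4.3%: not inflated, and slightly conservative as r grows.

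**The case against.** **The two sections need not conflict.** A reader might infer a flat contradiction: eCBs always in the model in one section, and in only if significant in another. The documents do not support that. Aim 3 introduces the mediation model for its own question, so eCBs could be fixed terms there and conditional covariates in an Aim 1 comparison. This objection stands. The sections are ambiguous together, and on this reading Aim 1 has no stated model at all.

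**Expected Outcomes may already describe a robustness check.** Its remark on adjustment can be read as a phase effect first and an adjusted one second. That is a fair reading, but the sentence states an expectation and does not say which result is Aim 1.

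**The sizes are assumed.** This stands. The anchor matters too: holding the adjusted effect at 0.30 makes the total 0.30 − 0.4 × 0.5 = 0.10, instead of raising the adjusted effect to 0.50. The direction and the gap of 0.20 are the same. The plan expects a phase shift for anandamide only, so the argument does not extend to 2-AG.

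**The power loss is slight.** This stands at modest correlations. A 15-point loss appears only at r = 0.7, which nothing in the documents supports. Participants also says the groups will be matched on drug use, which makes a significant difference on that variable less likely still.

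**Some listed measures may respond to phase.** Mood, cortisol and blood pressure are taken on session day within the assigned phase. The power argument therefore fits best for characteristics fixed before assignment, such as prior drug use.

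**Conclusion.** The concern holds as an undefined Aim 1 effect combined with a data-dependent covariate rule. That the plan states no Aim 1 model, does not choose between the total and the eCB-adjusted effect, and fixes no covariates needs no assumption. The numerical consequence does. It requires that phase raises AEA, that low AEA enlarges the THC response, and that AEA enters with a drug interaction or on a change score. In the illustration the total is 0.30, the adjusted effect 0.50, and the rule averages 0.43 to 0.44, triggering in about 47% of trials. With no AEA shift, or with a person-level main effect only, there is no difference.

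The power point is secondary: nil at r = 0, about 1 to 2 points at r = 0.3 and about 5 at r = 0.5. A reader might infer that choosing covariates by significance biases the phase comparison or inflates type I error in general. For variables that phase does not affect, it does neither. This should be corrected before unblinding; confidence is moderate because the effect sizes are not in the documents.

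**What to change.** Delete the significance rule from the section on potential problems, and add to Statistical Analyses:

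> Aim 1 estimates the total effect of assigned phase on the THC-minus-placebo response. AEA and 2-AG are not in this model, whatever the observed group differences. Covariates are fixed before unblinding: the session's pre-capsule value of the outcome, and past-30-day cannabis use with its drug interaction. The model for the post-capsule values has drug, phase, drug-by-phase, time and session order, with random effects for woman and for session within woman (or with post-capsule time points averaged within session). A model adding drug-by-AEA and drug-by-2-AG is reported as a labelled eCB-adjusted sensitivity analysis. The association of the response with measured baseline estradiol is a separate, stated Aim 1 analysis.

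Aims 2 and 3 keep their eCB terms. The estradiol sentence preserves what Aim 1 and the Approach promise. Cannabis use is proposed because Significance names its frequency as a source of variation in THC effects.

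The session-level random effect is essential. With 4 or 5 unaveraged time points, only a woman intercept, and session variance 0.25 to 1 times the residual variance, simulated type I error was 14% to 32%, against about 5% with averaged time points. Coding the pre-capsule value as a deviation from the woman's own mean is optional: drug-by-phase averaged 0.303 raw and 0.304 with deviation coding.

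If the investigators prefer the eCB-adjusted effect for Aim 1, they can say so and label the total effect as secondary.

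The cost is wording and a few degrees of freedom, about 0.3 points of power per useless covariate (20.8% to 20.5% at d = 0.3). No new data are needed, since pre-capsule values and drug-use history are already collected.
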